Subjects may withdraw from the study at any time without penalty and for any reason without prejudice to their future medical care. In all cases, the reason(s) for withdrawal, including the primary reason, must be recorded on the case report form (CRF). If a subject is prematurely withdrawn from the study for any reason, the investigator must make every effort to perform the evaluations described for the early termination/follow up visit (in clinic) and a further follow up contact (either by telephone or in clinic) 7 to 14 days later. Subjects who withdraw due to lack of efficacy (Cohort 3) or adverse events which may be attributed to double blind treatment will not be replaced.

Cohort 3 patients who withdraw due to personal reasons, poor compliance, other protocol deviations or are lost to follow up may be replaced until at least 30 evaluable patients have completed the study.

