### 5.3. FULL ANALYSIS SET (FAS)

The FAS will include all randomised subjects who receive at least one application of investigational medical product (IMP). Subjects will be included in their randomised treatment group even if they receive the wrong IMP. This population will be used for the primary efficacy analysis and most other analyses for efficacy and exploratory endpoints.

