### 6. GENERAL ASPECTS FOR STATISTICAL ANALYSIS

#### 6.1. GENERAL METHODS

All statistical tests for Cohort 3 will be 1-sided at the 0.05 level of significance and accompanied by a 2-sided 90% CI. There will not be any adjustments for multiple comparisons. No statistical testing will be performed with the data from Cohorts 1 and 2.

All summaries and listings will be presented by treatment group and by cohort. For Cohorts 1 and 2, adverse events and pharmacokinetic data will be presented by treatment group and BSA treated (10%, 40% and overall) to assess whether BSA impacts this data.

Only on-treatment records will be summarised for post-baseline visits, except follow-up, unless stated otherwise. A record is considered on-treatment if it is on or before the date of last study medication plus 1 day.

Continuous variables will be summarised using the number of observations (n), mean, standard deviation (SD), 95% Confidence interval (CI) of mean, median, minimum, and maximum. Geometric mean and coefficient of variation (CV) will be included for PK parameters, where appropriate. Categorical variables will be summarised using frequencies and percentages. The number of missing values will be presented in summary tables. The missing count will not include

SAP Version v2.0 Page 22 of 43

Date: 16th March 2017

subjects who have discontinued at earlier visits.

Unless otherwise specified, the estimated mean and median for a set of values should be printed out to 1 more decimal place than the original values, and standard deviations should be printed out to 2 more decimal places than the original values. The minimum and maximum should report the same number of decimal places as the original values. The coefficient of variation will always be reported as a percentage to 1 decimal place. Percentages will be displayed with 1 decimal place; except percentages will not be presented when the count is zero and 100% will be presented as an integer.

Unless stated otherwise, baseline will be defined as the last non-missing measurement prior to administration of the first dose of IMP.

In by-visit summary tables the baseline will be summarised using all available data, but also for each visit using only the baseline data from subjects with available data at the visit; hence the mean change from baseline will equal the mean visit value – mean baseline value.

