### 6.2.1. Efficacy Data

Missing efficacy data for Cohort 3 may result from:

- subject discontinuing from the study
- for data collected at the site the assessment may have been missed

For the sensitivity analysis of the primary efficacy endpoint missing values will be imputed using Markov Chain Monte Carlo (MCMC) multiple imputation methods. Means and variances from the

SAP Version v2.0 Page 23 of 43

Date: 16th March 2017

available data will be used to determine the MCMC starting values; imputed values will be selected with maximum likelihood methods. Initially, 200 MCMC runs will be generated before selecting the first imputed data set. An additional 24 data sets will be generated, separated by 100 iterations of the MCMC. The number of data sets may be increased if the analyses are not found to be sufficiently stable with respect to standard errors and p-values. Randomisation seed numbers will be specified for the MCMC run to ensure consistency and repeatability. These imputations will be performed separately within each treatment group.

The MCMC imputation assumes that data are missing at random.

To assess the influence of missing data several sensitivity analyses will be conducted for the primary efficacy endpoint, including a last observation carried forward (LOCF) analysis and worst case imputations when the missingness is considered informative; e.g. subject withdrew due to lack of efficacy. Details regarding which approaches will be used are in Section 8.1.1.

Missing categorical data will generally be considered as a non-response when dichotomizing responses for logistic modelling. Specific details are described in Section 8.

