#### 8.1. PRIMARY EFFICACY ENDPOINT AND ANALYSIS

The primary endpoint is the percentage change from baseline to Week 2 in the EASI score. Baseline will be taken as the last non-missing measurement prior to administration of the first dose of IMP, this should be Day 1 for the primary endpoint.

The observed percentage change from baseline to Week 2 in the EASI score will be analysed for the FAS with an Analysis of Covariance (ANCOVA) model that includes baseline score as a covariate and treatment (ZPL521 or placebo). The treatment effect will be estimated with the difference between the least square means (LS means), defined as ZPL521 - placebo.

The ANCOVA analysis assumptions will be checked by evaluating the model residuals. A Shapiro-Wilks test will be performed on the residuals; a p-value > 0.1 will be considered proof of normality. If the Shapiro-Wilks p-value is  $\leq 0.1$ , the residual plot will be evaluated for symmetry. If the evaluation of residuals indicates a problem with the model assumptions, a transformation of the data will be considered, including a rank-transformation of the data.

The EASI score will be summarised by treatment and visit for the FAS with observed data. Summaries will present the descriptive statistics for baseline, change from baseline and percentage change from baseline data.

Patient profile plots by treatment group, of the percentage change from baseline in EASI score will also be presented. Note that only observed data will be included in these plots; i.e. no imputations will be used.

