### 8.1.1. Sensitivity Analyses of the Primary Endpoint

The robustness of the primary analysis will be evaluated by repeating the primary analysis with

SAP Version v2.0 Page 28 of 43

Date: 16th March 2017

the per-protocol analysis set.

In addition, the following sensitivity analyses will be conducted using the FAS:

- an analysis where missing values will be imputed using MCMC multiple imputation methods (see Section 6.2.1). These imputations will be performed separately within each treatment group.
- an analysis using a worst case imputation for missing data considered as 'informative'.
   Missing data will be reviewed by the study team to identify situations where the
   missingness is considered informative; e.g. subject withdrew for lack of efficacy. In these
   situations the Week 2 score will be taken as equal to the worst score recorded for either
   treatment group. For the 'non-informative' values the MCMC imputed values will be
   used. Note, the worst case imputation i.e. worst score, will occur after the MCMC values
   have been generated.
- an analysis using an LOCF method for handling missing data

In addition, the EASI score will be summarised by treatment and visit for the FAS with MCMC imputation data. For this summary, the mean of the imputed data for a subject is used in the calculation. Hence when multiple imputations are performed for the analysis, a missing data point will be estimated with the mean of the multiple different imputations; this individual mean will be used to calculate the overall treatment summary statistics.

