### 14. INDEX OF TABLES

The following tables are planned to be generated and numbering is indicative only and may be updated for final reporting based on CSR requirements.

Table Number	Title	Cohort	Population
14.1.1.1	Screened Subject Disposition by Cohort	1,2,3	Screened
14.1.1.2	Subject Disposition by Cohort	1,2,3	Randomised
14.1.3.1	Demography by Cohort	1,2,3	FAS
14.1.3.2.1	Cohort 2: Baseline Characteristics	2	FAS
14.1.3.2.2	Cohort 3: Baseline Characteristics	3	FAS
14.1.3.3	Medical History by Cohort	1,2,3	FAS
14.1.4.1	Prior Medications by Cohort	1,2,3	SAF
14.1.4.2	Concomitant Medications by Cohort	1,2,3	SAF
14.1.4.3.1	Prior Emollient Medications by Cohort	2,3	SAF
14.1.4.3.2	Concomitant Emollient Medications by Cohort	2,3	SAF
14.1.5.1	Study Drug Exposure by Cohort	1,2	FAS
14.1.5.2	Cohort 3: Study Drug Exposure	3	FAS
14.2.1.1	Cohort 3: EASI by Visit	3	FAS
14.2.1.2	Cohort 3: EASI by Visit with Multiple Imputation	3	FAS
14.2.1.3	Cohort 3: ANCOVA of Percent Change from	3	FAS
	Baseline in EASI at Week 2: Observed Case		
14.2.1.4	Cohort 3: ANCOVA of Percent Change from	3	PP
	Baseline in EASI at Week 2: Observed Case		
14.2.1.5	Cohort 3: ANCOVA of Percent Change from	3	FAS
	Baseline in EASI at Week 2: Multiple Imputation		
14.2.1.6	Cohort 3: ANCOVA of Percent Change from	3	FAS
	Baseline in EASI at Week 2: LOCF		
14.2.1.7	Cohort 3: ANCOVA of Percent Change from	3	FAS
	Baseline in EASI at Week 2: Worst Case		
	Imputation		
14.2.1.8	Cohort 3: ANCOVA of Percent Change from	3	FAS
	Baseline in EASI Over Time: Observed Case		
14.2.1.9	Cohort 3: ANCOVA of Percent Change from	3	FAS
	Baseline in EASI at Week 2 by Baseline EASI:		
	Observed Case		
14.2.2.1.1	Cohort 3: EASI-50 by Visit	3	FAS
14.2.2.1.2	Cohort 3: Logistic Regression of EASI-50	3	FAS
14.2.2.2.1	Cohort 3: EASI-75 by Visit	3	FAS
14.2.2.2.2	Cohort 3: Logistic Regression of EASI-75	3	FAS
14.2.2.3.1	Cohort 3: EASI Component Erythema by Visit	3	FAS
14.2.2.3.2	Cohort 3: ANCOVA of Percent Change from	3	FAS
	Baseline in EASI Component Erythema Over		
	Time: Observed Case		

SAP Version v2.0 Page 39 of 43

Date: 16th March 2017

		- 1 .	
Table Number	Title	Cohort	Population
14.2.2.4.1	Cohort 3: EASI Component oedema/papulation by Visit	3	FAS
14.2.2.4.2	Cohort 3: ANCOVA of Percent Change from	3	FAS
14.2.2.4.2	Baseline in EASI Component	3	17.5
	oedema/papulation Over Time: Observed Case		
14.2.2.5.1	Cohort 3: EASI Component Excoriation by Visit	3	FAS
14.2.2.5.2	Cohort 3: ANCOVA of Percent Change from	3	FAS

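### SAP 8.1.1 averages the imputations within each patient before summarising, so the 95% CI in Table 14.2.1.2 is too narrow whenever EASI values are missing

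*SAP*

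**What the plan says.** SAP 6.2.1 plans MCMC multiple imputation by treatment group. After the first imputed data set, "An additional 24 data sets will be generated, separated by 100 iterations of the MCMC", which makes 25.

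SAP 8.1.1 then adds an EASI summary by treatment and visit on the imputed data for the FAS. For that summary "the mean of the imputed data for a subject is used in the calculation", and "this individual mean will be used to calculate the overall treatment summary statistics". SAP section 14 lists it as Table 14.2.1.2, "Cohort 3: EASI by Visit with Multiple Imputation".

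SAP 6.1 sets the content of continuous summaries: the number of observations, the mean, and "standard deviation (SD), 95% Confidence interval (CI) of mean, median, minimum, and maximum". For the companion observed-data summary (Table 14.2.1.1), SAP 8.1 states: "Summaries will present the descriptive statistics for baseline, change from baseline and percentage change from baseline data". I assume the imputed-data table has the same layout.

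Nothing in the SAP exempts Table 14.2.1.2 from the CI, reduces n for imputed values, or restores the between-imputation variance. SAP section 12 (changes from the protocol) does not mention it.

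**The concern.** Multiple imputation keeps several draws for each missing value so that their spread carries the uncertainty about that value. Averaging the draws first leaves one filled-in number per patient, and the usual formula then treats that number as measured. The standard error shrinks in two ways: the averaged values vary less than real observations would, and n is the full arm size although some patients contributed no measurement.

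Tables 14.2.1.1 and 14.2.1.2 will be read side by side. If the imputed-data table usually shows the tighter interval, a reader may conclude that imputation added precision, when the missing values in fact took information away. The effect is largest in the 10-patient placebo arm.

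The scope is limited. The mean is the same under averaging and under Rubin's rules. With complete EASI there is no error. No test or between-arm comparison uses this table. The observed-case ANCOVA (14.2.1.3) and the multiple-imputation ANCOVA (14.2.1.5) are separate analyses and are not criticised here.

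**Working it through.** **Inputs from the documents.** Arms of 20 and 10, difference 30 points, SD 30 for the percentage change, 1-sided 5% (Protocol 8.9, SAP 3.3). M = 25 imputations, done separately by arm (SAP 6.2.1, 8.1.1).

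**The plan's own figure.** The documents give no width or coverage for this CI. The related figure is the 80% power. The noncentrality is 30 / (30 × √(1/10 + 1/20)) = 2.58. The noncentral t gives 80.9% with 28 df and 80.8% with 27 df (ANCOVA); the normal approximation gives 82.6%. The stated 80% reproduces, so the planning SD and arm sizes are used below.

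**Direction, by algebra.** Write patient i's value in imputed data set m as the patient's average plus a deviation d_i(m). The deviations sum to zero over m, so the cross term vanishes and

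mean over m of S²(data set m) = S²(averaged values) + mean over m of S²(d(m)).

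Hence S²(averaged)/n ≤ W, the mean within-imputation variance of the group mean. Rubin's total variance is T = W + (1 + 1/25)B = W + 1.04B, where B is the between-imputation variance. The averaged-data standard error is therefore below Rubin's whenever the imputations vary. Baseline is fixed for each patient, so this holds for the score, the change and the percentage change.

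**Effect of counting imputed patients.** At SD 30, ten real observations give a half-width of 2.262 × 30/√10 = 21.5 points and eight give 2.365 × 30/√8 = 25.1. With 2 of 10 missing, the SAP rule uses the first formula on a set of values that is, if anything, less spread out.

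**Size, by simulation.** Assumed, because the documents do not say: correlation 0.75 (AR(1)) over Days 5, 8, 10 and 15; lost patients miss Days 10 and 15; three loss rules (worst Day 8 first, loss more likely with a worse Day 8, random); two normal imputation models; Jeffreys prior. There were 20,000 trials per cell. The SAP interval uses t with n−1 df; the comparator is Rubin's rules with Barnard-Rubin df. With complete data the CI covers 95.1%.

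Placebo arm (n = 10), Week 2:

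| Missing | Coverage of SAP CI | SE below true SD of the mean by | Half-width ÷ Rubin |
|---|---|---|---|
| 1 | 93% | 6-8% | 0.83-0.87 |
| 2 | 88-91% | 14-18% | 0.67-0.77 |
| 3 | 83-88% | 20-31% | 0.53-0.67 |

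The SE column does not depend on Rubin's rules. For worst-first loss under one model, the root mean square SE divided by the SD of the group mean over trials is 9.65/10.32 = 0.935, 10.02/12.20 = 0.821 and 11.33/16.45 = 0.689.

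Placebo half-widths in points:

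| Missing | SAP rule | Observed data only | Rubin |
|---|---|---|---|
| 2 | about 20 | 22-24 | 26-31 |
| 3 | 19-21 | 24-26 | 29-42 |

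With 2 missing, the SAP interval is narrower than the observed-data interval in 75-96% of trials. Rubin's rules cover 96-98%.

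Over correlations 0.5-0.9 and two priors, placebo coverage is 92-94 / 88-93 / 82-91% with 1 / 2 / 3 missing. In the active arm (n = 20) with 1 / 2 / 4 missing it is 94 / 92-93 / 89-91%.

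**Independent check.** A simpler simulation used one earlier covariate, random loss, correlations 0, 0.5 and 0.8, and 6,000 runs per cell. Placebo coverage was 91.9-93.6 / 88.2-92.7 / 83.1-90.0% with 1 / 2 / 3 missing. The averaged-data SE was below Rubin's in every run.

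**SD.** In the main simulation the median placebo SD with 1-3 missing runs from 8% below to 1% above the complete-data value. In the simpler one the mean ratio is 2-9% low with 1-2 missing and up to 14% low with 3. The point rests on the CI, not the SD.

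**The case against.** The direction is not in dispute. The case against concerns weight, size and remedy.

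- **Weight.** This is one statistic in one supplementary table, and it goes wrong only if data are missing. Inference about missing data comes from the ANCOVAs in Tables 14.2.1.5 to 14.2.1.7. The SAP states no purpose for this summary, and how a reader would take it is conjecture. All of this stands, and it limits the importance of the point.
- **Early termination.** Protocol 6.6 asks for an EASI at early termination, and SAP 6.3 assigns an on-treatment visit of that kind to the nearest scheduled visit where possible, so fewer values may be missing than simulated. With 2 of 10 placebo values lost at random, keeping Day 10 raises coverage from 90.4% to 91.8%; with 3 lost, from 88.0% to 90.2%. The error is smaller but remains.
- **Replacement.** Under Protocol 4.8, some Cohort 3 withdrawals "may be replaced until at least 30 evaluable patients have completed the study". That adds observed patients but does not remove the missing value, because SAP 5.3 says "The FAS will include all randomised subjects who receive at least one application of investigational medical product". With 12 placebo patients and 2 missing at random, coverage is 91.1%, or 93.4% with Day 10 kept. Withdrawals for lack of efficacy or treatment-attributable adverse events are not replaced.
- **Remedy.** Removing the CI, or footnoting it, would answer the stated fault, and the Rubin interval over-covers somewhat. The first part is fair, except that n and SD printed together let a reader rebuild the same interval. The number imputed can also be found by subtraction between the two tables, although SAP 6.1 leaves earlier discontinuations out of its missing count.
- **Assumptions.** Dropout, correlation, imputation variables and prior are all assumed, and only the Week 2 percentage change was simulated. This bears on the size, not on the direction, which is algebraic.

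**Conclusion.** The point holds. As written, SAP 8.1.1 with SAP 6.1 yields a 95% CI in Table 14.2.1.2 that is too narrow at any visit with imputed EASI. This is certain in direction and does not depend on the simulation settings.

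The size depends on how many values are missing, which the documents do not predict. One missing value costs 1-2 points of coverage, which is minor. Two or three missing of 10 in the placebo arm is material, with coverage in the high 80s to low 90s or below and an interval usually tighter than that from the observed data alone. The lowest figures need 3 of 10 lost and either worst-first loss or earlier visits that predict Week 2 poorly. Early-termination visits and replacement soften the effect without removing it.

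It should be corrected because the SAP prescribes a wrong standard error in a planned efficacy table. It does not threaten the primary result.

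**What to change.** Replace the last two sentences of SAP 8.1.1. For Table 14.2.1.2, compute the mean and its standard error in each of the 25 imputed data sets, combine them by Rubin's rules with small-sample degrees of freedom, and present the combined mean, SE and 95% CI with the numbers observed and imputed at each visit. Leave the SD, median, minimum and maximum to the observed-data Table 14.2.1.1.

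A simpler alternative is to show only the mean and the two counts in Table 14.2.1.2, with no SD or CI.

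Either is a wording change before database lock, as SAP section 2 allows. It needs no new data, alters no test and needs no protocol amendment, because Protocol 8.2 leaves missing-data handling to the SAP. The cost of the first option is that, with separate imputation in an arm of 10, the Rubin interval is wide and slightly conservative (96-98% coverage under the Jeffreys prior, and up to 99.8% under a regression-type prior).

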### 8.1.2. Additional Analyses of the Primary Endpoint

The percentage change from baseline to Day 5, Day 8 (Week 1) and Day 10 will also be analysed for the FAS using the same approach as for the primary analysis.

Additional summaries and analyses of the Week 2 data will be performed for the subgroups detailed in Section 6.5. These analyses will be based on the FAS and will be the same as the primary analysis.

### 8.2. SECONDARY ENDPOINTS AND ANALYSIS

#### 8.2.1. EASI-50 and EASI-75

The proportion of subjects who achieve an EASI-50 response will be summarised in the FAS with counts and percentages by treatment group at each visit. The number of missing values will also be presented.

An exact logistic regression analysis will be performed at Week 2. The model will include treatment and baseline EASI score. The odds ratio, p-value and associated exact 90% CI will be presented. Subjects with missing responses will be counted as non-responders.

The proportion of subjects who achieve an EASI-75 response will be analysed in the same way as described for the EASI-50.

SAP Version v2.0 Page 29 of 43

Date: 16th March 2017

The cumulative proportion of subjects achieving a  $\ge x\%$  reduction in EASI at Week 2 will be plotted against x, with different lines for each treatment group. Subjects with missing data will be regarded as having the worst change from baseline and labelled as such on the plot. Horizontal reference lines will be drawn that relate to the 0, 25, 50 and 75% reductions in EASI scores.

